16.1.1.2 Parameters

- PK Parameters for M254 as defined in Table 1: PK Parameters
- PK Parameters for total IgG (Immunoglubulin G) changes from baseline as defined in Table 1: PK Parameters

Table 1: PK Parameters

Parameter	Description	Part A Part B Part C F		Part D	SAS Programming	
		In all par	ts WNL in	Notes		
		• A • C to	bsolute v hanges fr otal IgG	alues for N om baseli	/1254 ne for	
C _{max}	Maximum serum concentration. Observed peak analyte concentration obtained directly from the experimental data without interpolation, expressed in concentration units	x	x	x	x	Cmax from WNL
t _{max}	Time to maximum serum concentration. First observed time to reach peak analyte concentration obtained directly from the experimental data without interpolation, expressed in time units.	x	x	x	x	Tmax from WNL
AUC _{0-last}	Area under the concentration-time curve (time 0 to time of last quantifiable concentration).	x	x	x		AUClast from WNL
AUC _{0-tau}	Area under the serum concentration-time curve over the dosing interval (time 0 to 15 days).				x	AUC0-tau from WNL where tau is equal to 15 days.
AUC _{0-inf}	Area under the serum concentration-time	x	x	x		AUCINF_obs from WNL

Parameter	Description	Part A	Part B	Part C	Part D	SAS Programming
		In all par • A • C te	rts WNL in Absolute v Changes fr otal IgG	puts are: alues for N om baseli	/1254 ne for	Notes
	curve (time 0 to infinity).					If AUC_%Extrap_obs >20% then parameter will be flagged, but not excluded from descriptive statistics
%AUC _{extra}	Percentage of estimated part for the calculation of AUC _{0-inf} . ((AUC _{0-inf} -AUC ₀₋ t)/AUC _{0-inf})*100%	x	x	x		AUC_%Extrap_obs from WNL
Kel	Terminal phase rate constant calculated by linear regression of the terminal log-linear portion of the concentration vs. time curve. Linear regression of at least three points is required to obtain a reliable k_{el} .	x	x	x		Lambda_z from WNL If Rsq adjusted ≤ .80 then parameter will be flagged, but not excluded from descriptive statistics.
t _{1/2}	Terminal phase half- life expressed in time units	x	x	x		HL_Lambda_z from WNL If AUC_%Extrap_obs >20% or Rsq ≤ .80 then parameter will be flagged, but not excluded from descriptive statistics.
Vz	Volume of distribution at terminal phase, calculated as CL/k _{el} .	x (M254 only)	x (M254 only)	x (M254 only)		Vz_obs from WNL
CL	Clearance, calculated as dose/AUC _{0-inf}	x (M254 only)	x (M254 only)	x (M254 only)		CL_obs from WNL
MRT	Mean residence time will be approximated to constant infusion rate, MRT = MRT _{total} - $T_{iv}/2$	x (M254 only)	x (M254 only)	x (M254 only)	x (M254 only)	MRTINF_obs from WNL

Parameter	Description	Part A	Part B	Part C	Part D	SAS Programming
		In all par • A • C	rts WNL in Absolute v Changes fr otal IgG	puts are: alues for I rom baseli	/1254 ne for	Notes
	Where T _{iv} . = infusion duration					

Note: AUCs will be calculated using linear up / log down, expressed in units of concentration x time.

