- PK sample is required prior to the start of infusion (on the day of the infusion).
- W Skip indicates that no assessments occur on these days.
- x ADA samples are collected at each pre-infusion and the final follow-up visit. Please refer to the lab manual for specific instructions.

Compound: M254 Protocol: MOM-M254-001

Protocol Date and Version:8 Global 28 April 2020

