## 4.1.4 Part D (USA sites included)

Part D is a repeated, fixed-dose, open-label study of M254. Any patients who participate in Parts B or C are allowed to participate in Part D if they meet inclusion criteria during screening for Part D. Part D may have up to 2 dose levels with up to approximately 15 to 34 ITP patients in total. The initial dose level for Part D will be less than or equal to the maximum tolerated dose, and it will be selected based on review of Part B data and available data from Part C. Following completion of Part C, the dose for new patients in Part D may be revised (the dose level will not be modified for patients who have already received at least 1 dose). Patients who have participated in Part B or C may be allowed to participate in Part D, prior to completion of randomization in Part C. New patients not in Part B or C may participate in Part D following complete randomization in Part C. The dose levels of M254 for Part D will be determined after analysis of available data from Part A, Part B, and Part C.

Following screening to confirm eligibility to participate (including rescreening patients who participated in Part B or C), M254 naïve patients will receive 4 doses of M254, and patients from Part B or C will receive 3 doses of M254 every 14 days. Patients in Part C may roll over into Part D by including any data after the last dose of IVIg or M254 in Part C for assessment of screening in Part D as long as those data are within the screening window specified. Please refer to Section 4.3.1 and Figure 1-5 for dosing details.

If the patient's platelet count has not returned to  $\leq 100 \times 10^9 / L$ , their platelet count will be monitored weekly until platelets return to  $\leq 100 \times 10^9 / L$ . If these conditions are not met, M254 will not be administered further. Patients will be followed for safety assessments and platelet counts up to at least 28 days post their last dose of M254. Safety will be reviewed by the SRC quarterly (or more often as required).

Blood for safety labs, PK, and PD will be collected as defined in the Schedule of Activities (Table 1-4).

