5.2 Secondary

Part A:

• To characterize the PK of a single intravenous administration of M254 at different doses in healthy volunteers

Part B:

• To characterize the PK of a single intravenous administration of M254 at different doses in ITP patients

Part C:

• To characterize the PK of a single intravenous administration of M254 at different doses

Part D:

- To characterize the PK of repeated intravenous doses of M254 in ITP patients
- To assess PD of repeated intravenous doses of M254 in ITP patients

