5.2.1 Secondary Endpoint

Part A, B and C:

• Measurements of PK parameters of M254 following the administration of a single intravenous dose

Part D:

- Measurements of PK parameters of M254 following the administration of a repeated intravenous doses
- Platelet response after repeated M254 administration

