16.2.2 Pharmacokinetic Parameters

PK parameters for M254 and total IgG changes from baseline will be estimated using non-compartmental methods.

The serum PK parameters will be estimated from the concentration-time profiles. In estimating the PK parameters for the M254, BQL values at the beginning of the profile will be set to zero. BQL values that occur after the first quantifiable point will be considered missing. Values that are embedded between BQLs, or quantifiable values occurring after two or more BQLs, will be set to missing at the discretion of the pharmacokineticist. In estimating the PK parameters for the total IgG negative change from baseline values will be included in the calculation of AUC. Actual sampling times, rather than scheduled sampling times, will be used in all computations involving sampling times. If the actual time or dose time is missing, the scheduled time may be substituted in order to calculate the PK parameter.

Continuous descriptive statistics (as defined in Section 9.1.3) will be used to summarize the calculated PK parameters by study part and treatment. For t_{max} , only median, min and max will be presented. If the total number of subjects per treatment is lower than 3 then the only descriptive statistics presented will be arithmetic mean, median, minimum and maximum

The points to be included in the k_{el} range will be determined by the pharmacokineticist after inspection of the semi-log concentration-time profiles. At least 3 points will be required to be used. The C_{max} data point will not be included.

Parameters based on adjusted r² below 0.80 or %AUC_{extra} above 20% will be flagged but not excluded from descriptive statistics.

Additionally, plots of dose normalized Cmax, AUC0-inf (individual values and geometric mean) versus dose level will be provided to evaluate dose proportionality.

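### For Part D, SAP Table 1 does not say which dose each PK parameter comes from and derives no first-to-last-dose comparison, so the repeated-dose PK objective is only partly answered

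*SAP*

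**What the plan says.** The Part D secondary objective is "To characterize the PK of repeated intravenous doses of M254 in ITP patients" (SAP 5.2), and its PK endpoint is "Measurements of PK parameters of M254 following the administration of a repeated intravenous doses" (SAP 5.2.1). Protocol 4.1.4 gives M254-naïve patients 4 doses, and "patients from Part B or C will receive 3 doses of M254 every 14 days".

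The Part D column of SAP Table 1 (16.1.1.2) ticks four parameters:
- Cmax, defined as "Observed peak analyte concentration obtained directly from the experimental data without interpolation";
- tmax;
- AUC0-tau, with the programming note "AUC0-tau from WNL where tau is equal to 15 days";
- MRT (M254 only), where "Mean residence time will be approximated to constant infusion rate" and the software output is MRTINF_obs.

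AUC0-last, AUC0-inf, %AUCextra, Kel, half-life, Vz and CL are not ticked for Part D. No Part has a trough or accumulation row. Under SAP 16.2.2, descriptive statistics "will be used to summarize the calculated PK parameters by study part and treatment". SAP 9.1.4 groups Part D by the total number of doses planned or received, and overall.

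Protocol Table D2 takes a PK sample before each infusion and follows the first and last dose on the same sampling pattern. Protocol Table 1-4 adds samples 14 and 28 days after the last dose.

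**The concern.** A repeated-dose PK objective normally asks whether exposure builds up, and by how much, between the first and last dose. None of the four parameters answers that unless it is computed at a named dose and compared with another. Table 1 names no dose and plans no ratio. Two of the four also sit awkwardly with dosing every 14 days: the AUC window is given as 15 days, and MRT uses a single-dose formula whose value depends heavily on where time zero is placed.

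At stake is whether the report can state, as a derived result, how far M254 accumulates and how last-dose exposure compares with single-dose exposure in Parts B and C.

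**Working it through.** **1. The plan's own figure.** The only number in the Part D column is tau = 15 days. The schedule gives 15 − 1 = 14, 29 − 15 = 14 and 43 − 29 = 14 days, so 15 is not reproduced. It may be a study-day label, since Day 15 is 14 elapsed days. Read literally, the window after a non-final dose includes the first day of the next dose. Under one compartment, for half-lives of 7 to 30 days, a 0–15 day window exceeds a 0–14 day window by about 14 to 16% for the first dose. For the last dose, where no further dose follows, the excess is 3 to 6%.

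**2. Is any comparison between doses planned?** SAP 9.1.4 and 16.2.2 summarise parameters by number of doses or by part and treatment, not by dose occasion. SAP 16.2.1 and Table 14.2.1.1 summarise M254 concentrations by time point for all Parts, which includes the Part D pre-dose and end-of-infusion samples. The raw pattern is therefore reported, but no exposure ratio is.

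**3. Size of accumulation.** The documents give no half-life; Protocol 6.6 says only that clearance should resemble that of endogenous IgG. I assume 7, 14, 21 and 30 days, one compartment, equal doses on schedule, and no M254 remaining at the first Part D dose. Let r = 2^(−14/t½). The last/first ratio is R(n) = 1 + r + … + r^(n−1). The share of AUC extrapolated beyond T days is 2^(−T/t½).

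| Assumed t½ (days) | r | R(3) | R(4) | AUC beyond 14 d | AUC beyond 28 d |
|---|---|---|---|---|---|
| 7 | 0.250 | 1.313 | 1.328 | 25% | 6% |
| 14 | 0.500 | 1.750 | 1.875 | 50% | 25% |
| 21 | 0.630 | 2.027 | 2.277 | 63% | 40% |
| 30 | 0.724 | 2.247 | 2.626 | 72% | 52% |

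**4. MRT.** MRTINF is AUMC over AUC, both extrapolated to infinity, so it rests on Kel. Even with 28 days of data after the last dose, the AUC share beyond the last sample passes the SAP's 20% flag level at assumed half-lives of 14 days or more. The AUMC share beyond T, (1 + kT)e^(−kT) with k = ln 2/t½, is larger: 24% to 86% at 28 days.

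If MRT is run from the first dose over the whole record, linear PK adds the mean dosing time:
- 4 doses: (0 + 14 + 28 + 42)/4 = 21 days;
- 3 doses: (0 + 14 + 28)/3 = 14 days.

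Subtracting half the infusion time removes at most about 2 hours, since planned M254 infusions are limited to 4 hours (Protocol 5.2.1). If MRT is anchored to the last dose, carry-over bias is zero with one compartment and about 3 to 6% in the bi-exponential cases tried.

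**5. Baseline correction.** The statistical methods appendix (Deviations from the SAP) records that pre-dose M254 concentrations were observed and that PK parameters were then based on change from baseline. SAP 9.2.1 takes baseline in each period, and what counts as a period in Part D is not defined. If each infusion were a period, then in units of the first-dose peak the last-dose peak R(n) would lose its own trough r·R(n−1). Because R(n) = 1 + r·R(n−1), the result is 1 at every half-life. The Cmax ratio would show no accumulation whatever the truth.

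**The case against.** The strongest reply is that the information is not lost. Pre-dose and near-peak concentrations are listed, plotted and summarised by time point, and Protocol 9.3.3 plans a population PK analysis outside the main study report. The study is descriptive, and the endpoint asks only for PK parameters after repeated doses. This stands: a reader might infer that a two-fold build-up would be invisible or that the objective is unanswered, and the documents support neither. However, the Part D content of the population analysis is not described, and a visible rise in mean concentrations is not a within-patient ratio.

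A reader might also infer that Table 1 mixes doses, taking Cmax from the last and AUC from the first. The text does not say so. The AUC row refers to the dosing interval, and SAP 9.2.1 treats Part D by period, so a per-dose reading is open. The supportable statement is that the dose is not specified.

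A third inference is that MRT is invalid or cannot be computed. An unticked row means not reported, and SAP 16.2.2 sets the Kel point selection and the quality flags without restricting them to any Part. Late samples exist, and MRT anchored to the last dose is nearly unbiased. The difficulty is the missing anchor and the unreported quality measures.

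**Conclusion.** The point holds as a gap in the Part D parameter list. Table 1 does not state the dose for any Part D parameter and derives no measure of accumulation, so the secondary objective is only partly answered.

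On assumed half-lives of 7 to 30 days, the unquantified effect would be about 1.3 to 2.2-fold after 3 doses and 1.3 to 2.6-fold after 4. These figures depend entirely on the assumed half-life. Delayed doses would lower them, and M254 carried over from Part B or C would change the ratio in 3-dose patients. The 14- or 21-day shift in MRT does not depend on half-life, but it arises only if the whole record is used, which the SAP neither states nor excludes.

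**What to change.** In the Part D column of Table 1 and in SAP 16.2.2:
- Derive Cmax and AUC0-tau separately after the first and the last dose, and give last/first ratios of both.
- Report the pre-dose concentration before every dose.
- If values are baseline-corrected, use the baseline before the first Part D dose, so that accumulation is not subtracted out.
- Reconcile tau = 15 days with the 14-day dosing interval.
- Either restrict MRT to Parts A to C, or anchor it to the last dose and report Kel, half-life and %AUCextra with it.
- Do not derive CL as dose over interval AUC, because steady state is not assured after 3 or 4 doses. The fraction of steady state reached is 1 − r^n. At an assumed 21-day half-life, CL would be overstated by 1/0.8425 − 1 = 19% after 4 doses and 1/0.75 − 1 = 33% after 3.

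The cost is a few more derived parameters and table rows. No new samples are needed, because the first and last doses already share the same PK sampling and each has a 14-day sample.

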16.2 Pharmacokinetic Summaries

16.2.1 Pharmacokinetic Concentrations

In calculation of total IgG changes from baseline the absolute BLQ values will be set to $\frac{1}{2}$ LLOQ. Serum concentrations for M254 and absolute total IgG below the quantifiable limit (BQL) will be set to $\frac{1}{2}$ lower limit of quantification (LLOQ) in the computation of mean concentration values. Continuous descriptive statistics (as defined in Section 9.1.3) will be used to summarize the serum concentrations of M254 (absolute values) and total IgG (absolute values and changes from baseline). These data will be summarized as described in Section 9.1.4. CV will not be presented for changes from baseline summaries. If over $\frac{1}{2}$ the subjects in a given cell in the absolute values and the changes from baseline table and will instead display as BQL for the arithmetic mean, median and minimum. With the exception of maximum all other statistics will be missing.

Negative change from baseline values will not be imputed for the linear plots. For the semi-logarithmic plots negative change from baseline values will be considered nearly zero and show on the figure.

Linear and semi-logarithmic plots of the median M254 serum concentration (absolute values) and total IgG (absolute values and changes from baseline) by scheduled sampling time will be provided by study part and treatment with one panel per study part and one line per treatment. For Part D these plots will be provided for both planned and actual treatment summaries. These plots will show time in hours. The plots will match the summary table results and will not have an observation at a given time point if more than half of the subjects have values BQL.

Linear and semi-logarithmic plots of the combined individual serum concentration profiles by actual sampling time (spaghetti plots) will be provided for M254 (absolute values) and total IgG (absolute values and changes from baseline) by study part and treatment. For Part D these plots will be provided for both planned and actual treatment summaries.

Linear and semi-logarithmic plots of the individual M254 serum concentration (absolute values) and total IgG (absolute values and changes from baseline) by actual sampling time will be provided by part, treatment, analyte and subject. These plots will show time in hours. Individual plots will use the BQL handling procedure described below for "Pharmacokinetic Parameters".

Individual M254 serum concentration (absolute values) and total IgG (absolute values and changes from baseline) data will be presented together with descriptive statistics by part and treatment.

16.2.2 Pharmacokinetic Parameters

PK parameters for M254 and total IgG changes from baseline will be estimated using non-compartmental methods.

The serum PK parameters will be estimated from the concentration-time profiles. In estimating the PK parameters for the M254, BQL values at the beginning of the profile will be set to zero. BQL values that occur after the first quantifiable point will be considered missing. Values that are embedded between BQLs, or quantifiable values occurring after two or more BQLs, will be set to missing at the discretion of the pharmacokineticist. In estimating the PK parameters for the total IgG negative change from baseline values will be included in the calculation of AUC. Actual sampling times, rather than scheduled sampling times, will be used in all computations involving sampling times. If the actual time or dose time is missing, the scheduled time may be substituted in order to calculate the PK parameter.

Continuous descriptive statistics (as defined in Section 9.1.3) will be used to summarize the calculated PK parameters by study part and treatment. For t_{max} , only median, min and max will be presented. If the total number of subjects per treatment is lower than 3 then the only descriptive statistics presented will be arithmetic mean, median, minimum and maximum

The points to be included in the k_{el} range will be determined by the pharmacokineticist after inspection of the semi-log concentration-time profiles. At least 3 points will be required to be used. The C_{max} data point will not be included.

Parameters based on adjusted r² below 0.80 or %AUC_{extra} above 20% will be flagged but not excluded from descriptive statistics.

Additionally, plots of dose normalized Cmax, AUC0-inf (individual values and geometric mean) versus dose level will be provided to evaluate dose proportionality.

17.0 Pharmacodynamic Analysis

The platelet counts will be assessed in Part B, C and D. The analysis described below will be performed at the end of the study, it will not be included in the interim reports. This analysis will be performed on the FAS and repeated on the PP set.

17.1 Pharmacodynamic Variables

17.1.1 Platelet Counts

• Platelet counts

17.1.2 Platelet Parameters

A therapeutic platelet count is defined as $\geq 50 \times 10^9$ /L and an increase from baseline of $\geq 20 \times 10^9$ /L (this will be referred to as threshold in Table 2: PD Parameters).

• Platelet parameters as defined in Table 2: PD Parameters

Table 2: Platelet PD Parameters calculated in WinNonLin.

Parameter	Description	Absolute values	Changes from baseline	% changes from baseline	SAS Programming Notes
t _{onset}	Time to onset of a therapeutic platelet count. Time that the response first crosses the threshold coming from the direction of the baseline value.	x			Tonset from WNL
R _{max}	Maximum platelet count following dosing, maximum and percentage platelet count change from baseline. Maximum observed response value.	x	x	x	Rmax from WNL
t _{max}	Time to maximum platelet count following dosing. Time of maximum observed response value.	X			Tmax from WNL
D _{aboveT}	Duration of a therapeutic platelet count. Total time that Response >= Threshold.	x			Time_Above_T from WNL
t _{offset}	Time greater than T _{onset} at which the curve first crosses back to the baseline side of threshold.	x			Toffset from WNL

AUC _{0-14d}	Area under the change from baseline platelet count-time curve for 14 days.	x	AUC0-14 from WNL
AUC _{0-28d}	Area under the change from baseline platelet count-time curve for 28 days.	X	AUC0-28 from WNL

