The SRC will review all safety data from both crossover cohorts in Part C; however the initiation of Part D will proceed after the SRC reviews all safety data from Cohort 1 and the recommendation is to proceed with Part D. Dose escalation and continuation to the next study part may only occur when the SRC has given a positive recommendation and the Ethical Committee has given a statement of no objection, as per local requirement (where required).

Figure 1-4. Part C Study Schema

IVIg = Intravenous immunoglobulin; TBD = to be determined.

Patients will be followed for 28 days or until their platelet counts have returned to ≤15% above baseline levels and then crossed to the second period. Patients will again be dosed and followed for an additional 28 days with safety and platelet assessments.

Compound: M254 Protocol: MOM-M254-001

Protocol Date and Version:8 Global 28 April 2020

[figure not shown]

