## 4.1.2 Part B (USA sites included)

Initiation of any cohort in Part B will only proceed on the recommendation of the SRC after safety data from Part A Cohort 4 at the 60-mg/kg dose level has been reviewed and confirmed by SRC.

Part B is a single-ascending-dose, fixed-sequence, open-label part to assess safety, tolerability, PK, and PD of M254 followed by 1000 mg/kg IVIg in approximately 4 cohorts of 2 ITP patients per cohort. Planned doses include 60, 120, 250, and 500 mg/kg. Up to 2 additional cohorts may be added based on findings in prior cohorts to better understand the safety of M254 and/or to better understand the efficacy to assist with dose selection for Part C. The maximum dose for Part B will not exceed 500 mg/kg. (The no-observed-adverse-event-level [NOAEL] of 1000 mg/kg was determined in the toxicology study in cynomolgus monkeys.) Additional patients to dosing cohorts may be added on the recommendation of the SRC.

Following screening to confirm eligibility to participate, patients will be dosed with M254. Please refer to Section 4.3.1 and Figure 1-3 for dosing details. There will be a 14-day safety monitoring period between enrollment of the first and second patients in the 500 mg/kg cohort.

Safety and platelet assessments will be conducted initially out to Day 28 post M254 administration. Patients will receive a fixed dose of IVIg at 1000 mg/kg on Day 29 if the patients' platelet count returns to  $\leq 15\%$  above baseline level. Patients whose platelets have not returned to  $\leq 15\%$  above baseline dosing level by Day 28 will have platelet determinations weekly until platelets return to  $\leq 15\%$  above baseline, up to 56 days postdose. If these conditions are not met by Day 57, IVIg will be administered, as long as the patients' platelets have returned to  $\leq 50 \times 10^9/L$ . If the platelets have not returned to  $\leq 15\%$  above baseline and are  $\geq 50 \times 10^9/L$ , the patient will complete Follow-Up assessments and be discharged from Part B. After dosing with IVIg, safety and the other assessments listed in the Schedule of Activities will be conducted for 28 days following IVIg administration.

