#### 4.1.5 Study Duration for Participants

The total duration of study participation for each cohort in Part A will be up to 8 weeks; up to 4 weeks for screening and 4 weeks observation and follow-up. The total duration of participation in Parts B and C will be 12 to 20 weeks: up to 4 weeks for screening and 4 to 8 weeks for M254 period and 4 to 8 weeks for IVIg period based on platelet measurements returning to baseline as described above. The total duration of study participation in Part D will be 12 to 14 weeks: 4 weeks for screening and 8 (patients from Parts B or C) or 10 (M254-naïve patients) weeks observation and follow-up.

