9.5 TFL Layout

Report layout will be according to the PRA EDS – ICH E3 compliant – CSR Template. The layout of TFLs will be according to the PRA EDS standards.

No table shells will be provided. The TFLs will be provided in Adobe PDF format.

Format:

- Page size: A4
- Data in listings will be sorted by study part, cohort, site number (if applicable: each site on a new page), subject number and time point.
- Data in tables will be sorted by study part, treatment and time point.

- Column titles will be in title case letters.
- All tables and listings will be in landscape format.
- The treatment labels listed below will be used in the TFLs. Treatments will be sorted by investigational product (placebo then M254 then IVIg) then dose level (increasing mg/kg) then number of doses. These labels will be modified to account for the dose selected as part of dose escalation and the initiation of each part:

. . .

- Part A: ○ Placebo
- 3 mg/kg M254 HV (Healthy Volunteers)
- o 10 mg/kg M254 HV
- 30 mg/kg M254 HV
- o 60 mg/kg M254 HV
- o 120 mg/kg M254 HV
- 250 mg/kg M254 HV
- M254 HV total

Part B and C:

Data will be first presented by cohort and within cohort by treatment period according to following layout:

60 mg/kg M254		120 mg/kg M254		Total				
M254 period	IVIg period	Diff	M254 period	IVIg period	Diff	M254 period	IVIg period	Diff
XXX	XXX	XXX	XXX	XXX	XXX	XXX	XXX	XXX
XXX	XXX	XXX	XXX	XXX	XXX	ххх	XXX	ххх
The fell	مالة سمامم بمماشيته	الأسد ملمما	he used in Deut	D.				

The following cohort labels will be used in Part B:

- o 60 mg/kg M254
- o **120 mg/kg M254**
- o 250 mg/kg M254
- o 500 mg/kg M254
- o Total

The following cohort labels will be used in Part C:

- XXX mg/kg M254 (XXX will be replaced by the actual dose level)
- Total

Pooled Part B and C:

- XXX mg/kg M254 (XXX will be replaced by the actual dose level)
- o M254 total
- o 1000 mg/kg IVIg

Part D (planned treatment):

- XXX mg/kg M254, 3 doses (XXX will be replaced by the selected mg/kg dose level)
- XXX mg/kg M254, 4 doses (XXX will be replaced by the selected mg/kg dose level)
- For the safety tables: XXX mg/kg M254 md (pooled)

Treatments in Part D will also be presented by actual treatment – that is if the number of doses differs from planned a separate summary will be presented.

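### SAP Table 2 sets no observation window for duration of platelet response (D_aboveT, t_offset), and the protocol contradicts itself on whether Part B follow-up is equally long after M254 and after IVIg

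*SAP*

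**What the plan says.** - SAP 17.1.2, Table 2, gives duration as "Duration of a therapeutic platelet count. Total time that Response >= Threshold". No end day is stated for it or for t_offset. In the same table the 28-day AUC is fixed: "Area under the change from baseline platelet count-time curve for 28 days". The other AUC is fixed at 14 days.
- SAP 17.2.2 derives the parameters from actual sampling times. SAP 9.1.5 drops unscheduled values from the statistics in Part A only, so nothing removes counts taken after Day 29 in Part B.
- Protocol 4.1.2: Part B is fixed-sequence, M254 then IVIg. A patient whose platelets have not come back to within 15% of baseline by Day 28 is counted weekly until they do, "above baseline, up to 56 days postdose". For the second period: "After dosing with IVIg, safety and the other assessments listed in the Schedule of Activities will be conducted for 28 days following IVIg administration". SAP 6.0 repeats this, and Protocol 8.1.3 places the final visit 29 ± 2 days after the last dose.
- Protocol 4.1.5, for Parts B and C, says otherwise: "4 to 8 weeks for IVIg period based on platelet measurements returning to baseline as described above".
- For Part C, Protocol 4.1.3 extends the second period under rules similar to those for the first dose. The note to Figure 1-4 mentions no extension: "Patients will again be dosed and followed for an additional 28 days with safety and platelet assessments".
- SAP 9.5, for Parts B and C: "Data will be first presented by cohort and within cohort by treatment period according to following layout". The columns are M254 period, IVIg period and Diff.

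**The concern.** A total time above threshold depends on how long one looks. If the two periods are watched for different lengths of time, part of the M254 minus IVIg difference reflects follow-up rather than drug. In Part B the order is the same for every patient, so a window difference falls wholly on the treatment contrast and always in the same direction.

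t_offset has a related gap. A patient still at threshold when the IVIg period closes has no observed return crossing, and the SAP has no rule for that case beyond not imputing missing values.

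At stake is how a descriptive result is read. Protocol 9.3.1 names duration of response as something to be presented, and a reader of the Diff column could not tell what interval it covers.

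**Working it through.** **1. The plan's own figure.** Protocol 4.1.5 states 12 to 20 weeks in total for Parts B and C. Screening 4 + M254 4 to 8 + IVIg 4 to 8 gives 4 + 4 + 4 = 12 and 4 + 8 + 8 = 20, so the figure reproduces. With the IVIg period held at 28 days, as in 4.1.2, the Part B maximum is 4 + 8 + 4 = 16 weeks. The two sections cannot both describe Part B.

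**2. Does the extension catch every long M254 response?** The SAP threshold is max(50, B + 20) × 10^9/L for baseline B. Extension is triggered above 1.15 × B. Eligibility requires B from 15 to below 50. The ratio of threshold to baseline is smallest at the upper end: (50 + 20)/50 = 1.4. The gap there is 70 − 57.5 = 12.5 × 10^9/L. So a patient still at threshold on Day 28 after M254 is always extended. Under 4.1.2 the same patient after IVIg is cut off.

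**3. One patient.** The largest window difference is 56 − 28 = 28 days. With 40-day responses to both products, counted from dosing, Diff = min(40, 56) − min(40, 28) = 40 − 28 = +12 days. If the other patient in a two-patient cohort has Diff 0, the cohort mean is 12/2 = +6 days.

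**4. On average.** The documents give no distribution of durations. Assume the same exponential duration with mean m for both drugs, ignoring time to onset. The artefact in the difference of period means is

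E[min(D, 56)] − E[min(D, 28)] = m × (e^(−28/m) − e^(−56/m)).

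At m = 14: 14 × (0.1353 − 0.0183) = 1.64 days. A simulation of 1,000,000 pairs gave 1.65 to 1.66.

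The paired Diff is smaller. Patients still high at Day 57 are discharged without IVIg, so the longest M254 responses have no pair. The last column is simulated, with within-patient correlation 0 and 0.6.

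| Assumed mean (days) | Share past Day 28 | Period means (days) | Paired Diff (days) |
|---|---|---|---|
| 7 | 2% | +0.13 | +0.11 to +0.12 |
| 10 | 6% | +0.57 | +0.41 to +0.47 |
| 14 | 14% | +1.64 | +0.87 to +1.10 |
| 21 | 26% | +4.08 | +1.36 to +2.07 |
| 28 | 37% | +6.51 | +1.56 to +2.79 |

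Every entry favours M254. All become zero if no response passes Day 28, or if both periods may run to 8 weeks and one cut-off applies.

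**5. Part C.** Suppose the Figure 1-4 note governed and the second period stopped at 28 days. With equal 14-day means the artefact is +1.6 days in one sequence and −1.7 in the other, averaging −0.02. Allocation is 5 to 5 in each cohort (SAP 6.2).

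**6. After the fix.** With a common 28-day cut-off, the artefact in period means is zero within simulation error. In the paired Diff a small negative remainder stays because of the Day 57 discharges: −0.05 to −0.28 day at m = 14, and −0.21 to −0.93 at m = 21.

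**The case against.** The strongest reply is that the unequal window is not settled. Protocol 4.1.5 gives the IVIg period 4 to 8 weeks, and its 20-week maximum depends on that. Followed in Part B, it removes the asymmetry. This stands, and it makes the effect conditional.

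The second reply is size. Protocol 2.2.1 expects IVIg responses seldom to last beyond 3 to 4 weeks, and the Overall Design text bases its 28 days on platelets being back near baseline by then. This also stands. The 40-day example is an illustration, not an expected case.

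Third, individual parameters are listed and individual profiles plotted (SAP 17.2), so one long responder would be visible. That helps a careful reader, but it does not tell them which interval the Diff covers.

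A reader might infer more than the documents support:

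- That Part B duration is biased outright. It is not, unless 4.1.2 is followed and responses pass Day 28.
- That the artefact steers later doses. SAP 17.0 keeps this analysis out of the interim reports, and dose escalation reports lie outside the SAP (7.2).
- That a secondary treatment comparison is compromised. The Part B platelet comparison is exploratory, duration is descriptive, and no hypothesis is tested.
- That Part C is biased. Its text applies similar rules in both periods, and its sequences balance.
- That Rmax and t_max share the defect. The peak is expected within 2 to 7 days, well inside either window.

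**Conclusion.** The point holds as a gap in definition with a conditional consequence. D_aboveT and t_offset have no stated window, and the protocol gives two incompatible lengths for the Part B IVIg period. If the Part B design text is followed, the difference in duration favours M254 whenever a response lasts past Day 28. The average effect is about 1 to 2 days at an assumed 14-day mean. The paired Diff sits at the lower end because the Day 57 discharges offset part of it. The bounds are zero if no response passes Day 28 and 28 days in a single patient.

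These sizes rest on equal exponential durations for both drugs, response counted from dosing, the SAP threshold, and baselines within the eligibility range. In Part C the most that could arise is a period artefact, which averages out across the two sequences when durations are equal. The Statistical Methods document appended to the SAP records other rules settled during analysis but gives no cut-off for duration, so the question remains open there too.

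**What to change.** In SAP Table 2, for the M254 versus IVIg comparison, derive D_aboveT and t_offset on the same 0-28 day window in both periods. Flag any patient still at or above threshold at the cut-off as censored, meaning a response lasting to at least 28 days. List durations beyond Day 28 separately. A 28-day window is available under either reading of the protocol and matches the longer AUC.

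Reconcile Protocol 4.1.2 with 4.1.5, and the Figure 1-4 note with 4.1.3, on how long platelets are followed after the second infusion. SAP 6.0 and its Figure 4 note should then agree.

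The cost is SAP wording, a short programming limit and a protocol clarification, with no new data. The downside is that durations beyond 28 days appear only in a listing. The small remainder from the Day 57 discharges stays in the paired Diff, so the number of patients without an IVIg period should be shown beside it.
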